10.6. Vital Signs

Vital signs (ie, sitting systolic blood pressure, sitting diastolic blood pressure, pulse rates, body temperature, weight, and height) will be summarized using the summary statistics defined in Section 6.2.1 and presented as described in Section 6.2.2.3. The summary will include the actual value and change from baseline. Vital signs results for Stages 1 and 2 have been reported in

iCSR-1 and will not be repeated in this SAP unless the underlying data have changed. Otherwise, the final CSR will reference the results in iCSR-1.

Vital signs data collected during Stage 2 Period 5 through Stages 3 and 4 to the DBL date will be analyzed on the Safety population. Per the schedule of assessments, vital signs were monitored at 0, 1, 4, 6, 12, and 24 hours after the infusion for Stage 3. Therefore, the analysis of vital signs will include summaries at these monitoring time points.

The incidence rates of values exceeding the PDLC criteria for vital signs defined in [Table 9](#) by parameter will be summarized altogether (over the duration from first dose in Stage 2 Period 5 through Stages 3 and 4 to the DBL date), not by visit. Unscheduled visits will be included in evaluating the PDLC summary. All vital signs data will be presented in data listings.

Table 9: Pre-defined Limits of Change Criteria for Vital Signs

Vital Sign	Criteria
Pulse (Heart Rate)	≥ 120 bpm at any time post-dose and ≥ 15 bpm increase from baseline at any time post-dose
	≤ 50 bpm at any time post-dose and ≥ 15 bpm decrease from baseline at any time post-dose
Systolic Blood Pressure	≥ 180 mm Hg at any time post-dose and ≥ 20 mm Hg increase from baseline at any time post-dose
	≤ 90 mm Hg at any time post-dose and ≥ 20 mm Hg decrease from baseline at any time post-dose
Diastolic Blood Pressure	≥ 105 mm Hg at any time post-dose and ≥ 15 mm Hg increase from baseline at any time post-dose
	≤ 50 mm Hg at any time post-dose and ≥ 15 mm Hg decrease from baseline at any time post-dose
Weight	Change: $> 5\%$ increase from BL
	Change: $> 5\%$ decrease from BL

Abbreviations: BL = baseline; bpm = beats per minute; mm Hg = millimeters mercury

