Study treatment for all subjects in Stage 3 will consist of AT2221 administered orally at 260 mg followed approximately 1 hour later by a single-dose IV infusion of ATB200 at 20 mg/kg (repeated every 2 weeks for up to 24 months).

Note: Subjects are required to fast at least 2 hours before and 2 hours after administration of oral AT2221.

Total Duration of Study:

- Screening: up to 4 weeks
- Stage 1 + Stage 2: 18 weeks
- Stage 3: 24 months
- Stage 4: Until completion or drug approval

Criteria for Evaluation:**Primary:**

Safety assessments:

- PEs
- Vital signs, including body temperature, RR, HR, and BP
- AEs, including IARs
- 12-lead ECG
- Clinical safety laboratory assessments: serum chemistry, hematology, and urinalysis

PK of plasma ATB200 and AT2221:

- Plasma GAA activity levels and total GAA protein concentrations PK parameters: maximum observed plasma concentration (C_{max}), time to reach the maximum observed plasma concentration (t_{max}), area under the plasma-drug concentration time curve from Time 0 to the time of last measurable concentration (AUC_{0-t}), area under the plasma-drug concentration time curve from Time 0 extrapolated to infinity ($AUC_{0-\infty}$), alpha- and beta-phase half-life ($t_{1/2}$), total clearance following IV administration (CL_T), and steady state volume of distribution (V_{ss})
- Ratios of plasma GAA activity levels and total GAA protein concentration C_{max} , AUC_{0-t} , and $AUC_{0-\infty}$ for all dose regimens
- Plasma AT2221 PK parameters: C_{max} , t_{max} , AUC_{0-t} , $AUC_{0-\infty}$, and $t_{1/2}$, apparent total clearance of drug following oral administration (CL_T/F), and terminal phase volume of distribution following oral administration (V_z/F) for each dose level
- Ratio of plasma AT2221 PK parameters: C_{max} , AUC_{0-t} , and $AUC_{0-\infty}$ for each dose level
- Exposure estimates from sparse plasma total GAA protein concentrations after at least 18 months on ATB200/AT2221 treatment in Cohorts 1 and 3 patients will be compared to exposures after the first and third doses of 20 mg/kg ATB200 + 260 mg AT2221.

Functional Assessments (performed at Baseline and every 3 months in Stage 3):

For Ambulatory Subjects:

- Motor Function Tests
 - 6MWT
 - 10-Meter Walk Test (10MWT)
 - Gait, Stairs, Gower, and Chair maneuver (GSGC)
 - Timed Up and Go (TUG)

- Muscle Strength Test
 - medical research criteria (MRC) and hand-held dynamometer for both upper and lower limbs
- PFTs

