Note: At least one of the 2 sentinel subjects will complete Period 5, Stage 2 dosing, and the safety data will be reviewed by the SSC, before any newly enrolled subjects in Cohorts 2 and 3 can be dosed. The first 2 subjects in Cohorts 2 and 3 will also serve as sentinel subjects for their respective cohorts.

In Stage 1 (Periods 1, 2, and 3), subjects will be dosed with single-ascending doses of ATB200 (5 mg/kg [Period 1], 10 mg/kg [Period 2], and 20 mg/kg [Period 3]).

Following the dosing of the 2 sentinel subjects for each study period in Stage 1, an evaluation of the available safety data (physical examination [PE], vital signs, adverse events [AEs], infusion reactions, electrocardiogram [ECG], and available locally performed laboratory tests) will be performed within 24 to 48 hours by the Amicus Medical Monitor and the investigators. The SSC will convene for a formal safety review when central safety laboratory data are available for both sentinel subjects at each dose level. If the SSC determines that there are no safety concerns that preclude dosing at the dose assigned for that period, 10 additional subjects will be enrolled and dosed.

Note: Vital signs will be monitored as detailed in [Table 9](#), [Table 10](#), [Table 11](#), [Table 12](#), and [Table 13](#). For PK Visits 3, 4, 5, 6, and 9, vital signs will be monitored at hours 0, 1, 4, 6, 12, and 24 after the start of infusion. During the 48-hour observation period, vital signs will be monitored, at a minimum, every 6 to 8 hours until the end of the 48-hour observation period.

The SSC will also convene for a safety review when safety data (including central laboratory safety data) for all subjects at all three Stage 1 dose levels are available.

In Stage 2 (after Visits 6 and 9), safety data from the 2 sentinel subjects will be reviewed by the SSC, and safety will be assessed after the first dose as for each period in Stage 1. If the SSC determines that there are no safety concerns that preclude additional dosing at 20 mg/kg ATB200 co-administered with 130 mg AT2221 (Visit 6) or 20 mg/kg ATB200 co-administered with 260 mg AT2221 (Visit 9), the remaining subjects in Cohort 1 will receive Stage 2 treatment.

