^a All study assessments will be performed on the day indicated for each period. Twenty-four-hour PK assessments will take place on the second day of each visit (see [Table 14](#)).

^b Sentinel dosing for the first 2 sentinel subjects during all periods and in all stages will be followed by safety review by investigators and Amicus Medical Monitor before dosing all the other subjects.

^c Sitting vital sign assessments will include measurement of body temperature, rate of respiration, heart rate, and systolic and diastolic blood pressures.

^d Vital signs will be monitored at hours 0, 1, 4, 6, 12, and 24 (Stage 1) and 0, 1, 4, 6, 11, and 25 (Stage 2). Vital signs should be measured after the blood draws for PK assessments if possible. A standard 12-lead ECG will be performed after infusion at all study visits and at the beginning and end of the infusion (approximately 4 hours after the start of infusion) for all PK visits.

^e Comprehensive physical examination at Screening and Visit 12; brief physical examination will be performed at other visits where indicated.

^f PROMIS assessments will be administered if a validated instrument is available for the country.

^g Blood sampling is to be performed before the infusion commences or AT2221 is dosed. The blood draw can be taken at the same time as clinical safety sample, which is described in the laboratory flowchart. Total GAA protein concentration may be measured as well, as assay sensitivity can be affected by GAA protein.

^h Three blood samples will be taken: one just prior to dosing of AT2221 (if applicable), one just prior to the start of infusion (preferably within 5 to 10 minutes prior to the start of infusion), and another approximately 2 hours or halfway through the infusion. For Screening and Baseline visits, the blood draws are to be spaced apart at time points similar to PK visit.

ⁱ At Screening, a sample will be obtained. At all other visits, a blood sample will be obtained for IgE determination if a subject has signs of infusion-related reaction or anaphylaxis (see [Section 11.1.3](#)). The sample should be obtained 6 to 8 hours after the onset of the reaction and at 24 hours for IgE measurement. A third sample is to be drawn immediately before the next administration of study drug. Total GAA protein concentration will be measured as well, as assay sensitivity can be affected by GAA protein.

^j The 24-hour PK sample for each PK assessment will be collected on the second day of each visit.

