^c Stage 4 begins after 2 years in Stage 3. Frequency of assessments is every 6 months.

^d Sitting vital sign assessments will include measurement of body temperature, rate of respiration, heart rate, and systolic and diastolic blood pressures.

^e Vital signs will be monitored at hours 0, 1, 4, 6, 12, and 24 for all PK visits. A standard 12-lead ECG will be performed after infusion at all study visits and at the beginning and end of the infusion (approximately 4 hours after the start of infusion) for all PK visits.

^f Comprehensive physical examinations will be performed at the first visit, and during the visits for Month 12, Month 24, and every assessment visit in Stage 4. Brief physical examinations will be performed at all other visits.

^g PROMIS assessments will be administered if a validated instrument is available for the country.

^h Blood sampling is to be performed before the infusion commences or AT2221 is dosed. The blood draw can be taken at the same time as clinical safety sample, which is described in the laboratory flowchart. Total GAA protein concentration may be measured as well, as assay sensitivity can be affected by GAA protein.

- ⁱ Three blood samples will be taken: one just prior to dosing of AT2221 (if applicable), one just prior to the start of infusion (preferably within 5 to 10 minutes prior to the start of infusion), and another approximately 2 hours or halfway through the infusion. For Screening and Baseline visits, the blood draws are to be spaced apart at time points similar to PK visit.
- ^j Sparse blood sampling for plasma total GAA protein will be performed for Cohort 1 and Cohort 3 patients at any one visit after at least 18 months but no more than 24 months of ATB200/AT2221 treatment at times indicated in [Table 15](#).
- ^k At Screening, a sample will be obtained. At all other visits, if a subject experiences anaphylaxis as defined in [Appendix 1](#) or a moderate to severe infusion reaction (in the opinion of the investigator), a blood draw is to be performed 6 to 8 hours after the start of the infusion reaction and at 24 hours for IgE measurement. A third sample is to be drawn immediately before the next administration of study drug. Total GAA protein concentration will be measured as well, as assay sensitivity can be affected by GAA protein.
- ^l The 24-hour PK sample for each PK assessment will be collected on the second day of each visit (see [Table 14](#)).

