10.2.6. Vital Signs, Weight, and Height

Sitting vital sign assessments will include measurement of body temperature, respiration, heart rate, and systolic and diastolic blood pressures at times noted in [Table 9](#), [Table 10](#), [Table 11](#), [Table 12](#), and [Table 13](#). During blood sample collection for PK assessments for Cohorts 1 and 3, vital signs will be taken after selected blood samples.

During Stage 3, the subject weight will be measured at 3 month intervals in all cohorts. This weight will be used to revise the dose calculation of ATB200 if there has been a change since the previous 3 month measurement.

During Stage 4, the subject weight will be measured at 6 month intervals in all cohorts. This weight will be used to revise the dose calculation of ATB200 if there has been a change since the previous 6 month measurement.

Note: For visits where a subject is administered a new ATB200 dose level for the first time, vital signs will be monitored for the first 12 hours after the start of infusion. During the 48 hour observations period vital signs will be monitored, at a minimum, every 6 to 8 hours until the end of the 48-hour observation period.

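### SAP 10.6 gives respiration rate no summary, and presents Cohort 3 PK-visit vital-sign times as a Stage 3-wide post-infusion schedule

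*SAP*

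**What the plan says.** On parameters, SAP 10.6 says: "Vital signs (ie, sitting systolic blood pressure, sitting diastolic blood pressure, pulse rates, body temperature, weight, and height) will be summarized", as actual values and changes from baseline. All vital signs data also go into listings. The protocol's list is different. Its synopsis gives the primary safety criterion as "Vital signs, including body temperature, RR, HR, and BP", and section 10.2.6 says: "Sitting vital sign assessments will include measurement of body temperature, respiration, heart rate, and systolic and diastolic blood pressures". The footnotes to Tables 9 to 13 repeat that content. Change from baseline in vital signs is a primary safety endpoint (12.1.1), and 12.4.4.3 promises by-visit values and changes for vital signs by cohort.

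On timing, SAP 10.6 covers data from Stage 2 Period 5 to database lock. It states "Per the schedule of assessments, vital signs were monitored at 0, 1, 4, 6, 12, and 24 hours after the infusion for Stage 3" and concludes that the analysis will include summaries at those times. It names no cohort. Under SAP 6.2.2.3 the results appear in four cohort columns, a pooled ambulatory column and a Total.

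Protocol Table 12 footnote e, for Cohort 3, reads: "Vital signs will be monitored at hours 0, 1, 4, 6, 12, and 24 for all PK visits". Protocol 8.2, for PK Visits 3, 4, 5, 6 and 9, reads: "vital signs will be monitored at hours 0, 1, 4, 6, 12, and 24 after the start of infusion".

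**The concern.** The SAP introduces its list as exhaustive, and its Introduction says that its analyses replace those in the protocol. A programmer who follows it will produce no table for respiration rate. Pompe disease leads to respiratory insufficiency, and protocol Table 19 lists tachypnea as a sign of a moderate infusion reaction. This is therefore a parameter that a safety reader would look for.

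The timing sentence attributes to the schedule something that the schedule does not contain. A table built on it would suggest that every Stage 3 cohort was measured at six set times, and that all six followed the infusion. A pooled or Total column could then rest mainly or wholly on the ERT-naive cohort. Readings taken during infusion would be labelled as post-infusion, in a report that also analyses infusion reactions by time after infusion (SAP 10.3.3.3).

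**Working it through.** There is no planned figure to reproduce. The check sets the two documents side by side.

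**Parameters**

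| Parameter | Protocol 10.2.6 vital signs | SAP 10.6 summary |
|---|---|---|
| Systolic pressure | yes | yes |
| Diastolic pressure | yes | yes |
| Heart rate / pulse | yes | yes |
| Temperature | yes | yes |
| Respiration | yes | **no** |

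One of five measured vital signs has no summary. SAP Table 11, which records departures from the protocol, has an entry for vital signs, but it concerns shift tables and does not mention respiration. SAP 10.6 also lists height, which the schedules measure only at Screening (Tables 9, 11, 12 and 13; Table 10 has no height row). Its change from baseline would therefore be empty.

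**Which Stage 3 schedules give set hours**

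| Schedule | Cohort | Set hours |
|---|---|---|
| Table 10 | 1 | none |
| Table 11 | 2 | none |
| Table 12, footnote e | 3 | 0, 1, 4, 6, 12, 24 at PK visits |
| Table 13 | 4 | none |

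Planned sizes in SAP Table 2 are 11, 4–6, 5 and 6–8. The total runs from 11 + 4 + 5 + 6 = 26 to 11 + 6 + 5 + 8 = 30. Cohort 3 is 5/30 = 17% to 5/26 = 19% of that. This is the share with set hours in a Stage 3 schedule. It is not a ceiling on who may have timed readings, because protocol 10.2.6 also calls for monitoring over the first 12 hours when a subject first receives a new ATB200 dose level. That rule sets no hours and no cohort limit. Day 1 of Stage 3 is a first ATB200 dose for Cohorts 2 and 4.

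**Time zero**

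Protocol 8.2, the synopsis and 10.2.6 all count vital-sign hours from the start of infusion. No section counts them from its end. Footnote e gives no time zero for vital signs, and Table 14 counts Cohort 3 PK sampling from AT2221 dosing, about 1 hour before infusion (13.3.2). With an infusion of about 4 hours (13.3.1), there are two possible clocks:

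- Start of infusion: the infusion runs from hour 0 to about hour 4. Hour 0 is its start, hour 1 is during it, and hour 4 is about its end.
- AT2221 dosing: the infusion runs from about hour 1 to about hour 5. Hour 0 is before it, hour 1 is its start, and hour 4 is during it.

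On either clock, none of hours 0, 1 and 4 falls after a completed infusion, so the post-infusion label is wrong for them whichever clock was used.

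**Cohort 1 Visit 9 (Period 5)**

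Protocol 8.2 and the synopsis give the last two times as hours 12 and 24. Table 9 footnote d gives hours 11 and 25 for Stage 2. These passages conflict and must be reconciled.

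**The case against.** The strongest reply is that little is lost. Respiration rate stays in the listings. Tachypnea reported as an adverse event or infusion reaction enters those summaries. Each summary reports its n beside the cohort columns, so a pooled column fed by one cohort would be visible. No hypothesis is tested. All of this stands and limits the harm. It does not supply the summary that protocol 12.4.4.3 promises, or make the timing sentence correct.

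Several stronger readings are tempting, and the documents do not support them:

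- A reader might infer that the SAP shifts every reading by the length of the infusion. The SAP copies the protocol's hour set, including hour 0, and nothing in it re-times data from the end of infusion. The fault is the label, and no size of shift can be given.
- A reader might infer that timed Stage 3 readings exist only for Cohort 3 on Day 1 and Week 4. The first-dose rule in 10.2.6 foresees others. That section also ties vital signs to PK sampling in Cohorts 1 and 3, and both cohorts have sparse PK sampling after at least 18 months of treatment.
- A reader might count hours 11 and 25 as times that match no SAP row. The SAP sentence is confined to Stage 3. Both hours are also Table 14 sampling times on the AT2221 clock, where hour 25 is about 24 hours from the start of infusion.
- A reader might fault SAP Table 9 for setting no respiration limit. Protocol Appendix 2 sets none either, so the two agree.

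On height, the synopsis does list it among Stage 3 safety assessments, so the SAP has a source for it. The consequence is only an empty change row.

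**Conclusion.** The point holds in two parts. First, respiration rate, one of the five measured vital signs and part of a primary safety endpoint, has no planned summary, and no recorded decision explains why. Second, SAP 10.6 misstates the Stage 3 schedule. The set hours belong to Cohort 3 PK visits (5 of 26 to 30 planned subjects), and describing them as post-infusion fits neither the protocol's stated time zero nor the AT2221 clock.

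This affects the completeness and labelling of safety tables. It does not affect any test or the data collected. It rests on the planned cohort sizes and on reading the list in SAP 10.6 as exhaustive, as its wording indicates. The Cohort 3 time zero remains open: the start of infusion is likely, but footnote e does not state it.

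**What to change.** In SAP 10.6:

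1. Add respiration rate to the by-visit value and change-from-baseline summaries.
2. Report height at baseline only. SAP 7.4 already includes it among the baseline characteristics.
3. Replace the post-infusion wording with time from the start of ATB200 infusion, after confirming which time zero was used for Cohort 3.
4. Present the timed summaries by cohort, for the cohorts and visits that have timed readings, without a pooled or Total column. Keep any first-dose timed readings taken in Cohorts 2 and 4 under protocol 10.2.6.
5. Reconcile the two sets of protocol hours for Cohort 1 Visit 9 before placing any Period 5 reading in a timed row. Confirm the list of Cohort 1 visits at the same time, because protocol 8.2 names Visit 9 but not Visit 11.

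The cost is revised wording and one more parameter in an existing table, from data already collected. The downside is a slightly longer table and no pooled timed column.

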10.7. Electrocardiogram Variables

Quantitative ECG results will be summarized for the actual value and absolute change from baseline values using the descriptive statistics described in [Section 6.2.1](#) and reported per the descriptions in [Section 6.2.2.3](#).

Electrocardiogram results for Stages 1 and 2 have been reported in iCSR-1 and will not be repeated in this SAP unless the underlying data have changed. Otherwise, the final CSR will reference the results in iCSR-1. Electrocardiogram data collected during Stage 2 Period 5 through Stages 3 and 4 to the DBL date will be analyzed on the Safety population.

For categorical ECG data, frequency counts and percentages will be presented. The number and percentage of subjects with ECG interpretations (recorded as: Normal/Abnormal, Not clinically significant/Abnormal, Clinically significant) as well as the specific clinical findings for the abnormal ECGs will be presented.

The incidence rates of values exceeding PDLC for ECG intervals defined in [Table 10](#) by parameter will be summarized altogether (over the duration from first dose in Stage 3 to the data cutoff date), not by visit. Unscheduled visits will be included in evaluating the PDLC summary. For the PDLCs, it is possible for subjects to appear in both categories for any parameter. All ECG data, including the interpretation of normal/abnormal and the specific clinical findings for the abnormal ECGs will be presented in data listings.

Table 10: Pre-defined Limits of Change Criteria for Electrocardiogram Values

ECG Parameter	Criteria	
PR interval (msec)	< 120 msec or \geq 210 msec	
QRS duration (msec)	\leq 50 msec or $>$ 120 msec	
QTcB interval (msec)	Change from baseline for QTcB and uncorrected QT: \leq 30 msec or $>$ 30 msec; \leq 40 msec or $>$ 40 msec Absolute post-baseline QTcB and uncorrected QT interval: \leq 450 msec or $>$ 450 msec \leq 480 msec or $>$ 480 msec \leq 500 msec or $>$ 500 msec	
QTcF interval (msec)	Change from baseline for QTcF and uncorrected QT: \leq 30 msec or $>$ 30 msec; \leq 40 msec or $>$ 40 msec Absolute post-baseline QTcF and uncorrected QT interval: \leq 450 msec or $>$ 450 msec \leq 480 msec or $>$ 480 msec \leq 500 msec or $>$ 500 msec	
Ventricular rate (bpm)	A decrease from reference \geq 15 bpm, and an absolute value $<$ 50 bpm	An increase from reference \geq 15 bpm, and an absolute value $>$ 120 bpm

Abbreviations: bpm = beats per minute; ECG = electrocardiogram; msec = millisecond; PR = PR interval (measured from the beginning of the P wave to the beginning of the QRS complex in ECG tracing); QRS duration = duration of the QRS complex; QT interval = a measure from the start of the Q wave to the end of the T wave in the heart's electrical cycle; QTcB = QT interval for corrected heart rate (using Bazett's formula: QT/RR^{1/2}); QTcF = QT interval for corrected heart rate (using Fridericia's formula: QT/RR^{1/3})

